### Vital Sign Reporting

For vital signs change from baseline will be summarized together with the number of subjects whose blood pressure and heart rate fall outside specified ranges. Furthermore, the number of subjects who decreases and increases in responses fall outside specified ranges will be summarized (for blood pressure only).

| Endpoint                   | Cutoff      |
|----------------------------|-------------|
| Systolic Blood Pressure    | <90         |
| SBP Increase from Baseline | ≥30         |
| SBP Decrease from Baseline | ≥30         |
| Diastolic Blood Pressure   | <50         |
| DBP Increase from Baseline | ≥20         |
| DBP Decrease from Baseline | ≥20         |
| Pulse                      | <40 or >120 |

At all visits, for replicates, the second PVR value should be reported. This should also be the smallest if done per protocol. This should be footnoted as follows: “Only the second PVR urine volume is reported in the summary tables in cases where a repeat PVR assessment is made”.

Visual Acuity (LogMAR units) and Accommodation (the distance for each eye at which vision becomes blurred – the mean of triplicate measurements), CBCL (Domain T Scores and Total Scores as captured in the CRF), GPT (Time to completion, Number of pegs dropped and Number of pegs correctly placed – by dominant/non-dominant hand and whether the 10-peg or 25-peg test was used, separately), Physical Exam and Weight will be summarized by visit and changes from baseline at each visit using descriptive statistics.

For Visual Acuity, LogMAR units will be derived from the Snellen ratios recorded on the CRF, as shown in the table below. The decimal is the Snellen ratio (whether it is recorded in metres or feet) expressed as a decimal and  $\text{LogMAR} = \text{Log}_{10}(1/\text{decimal})$  (recorded to 1 d.p.). Due to the limited space available in the CRF, the Snellen ratio ‘20/12.5’ will be recorded as ‘20/13’, however this should still be converted to a decimal value of 1.60 and a LogMAR value of -0.2 as shown in the table below. If the Snellen Visual Acuity has been recorded in any other format than those shown below, the appropriate conversion to decimal will be determined prior to database lock.

Table 3  
Equivalent visual acuity measurements

| Snellen visual acuity |        |        |         |                  |        |
|-----------------------|--------|--------|---------|------------------|--------|
| 20 ft                 | 6 m    | 4 m    | Decimal | MAR a | LogMAR |
| 20/640                | 6/192  | 4/128  | 0.03    | 32               | 1.5    |
| 20/500                | 6/152  | 4/100  | 0.04    | 25               | 1.4    |
| 20/400                | 6/120  | 4/80   | 0.05    | 20.0             | 1.3    |
| 20/320                | 6/96   | 4/63   | 0.063   | 16               | 1.2    |
| 20/250                | 6/76   | 4/50   | 0.08    | 12.5             | 1.1    |
| 20/200                | 6/60   | 4/40   | 0.10    | 10.0             | 1.0    |
| 20/160                | 6/48   | 4/32   | 0.125   | 8.0              | 0.9    |
| 20/125                | 6/38   | 4/25   | 0.16    | 6.3              | 0.8    |
| 20/100                | 6/30   | 4/20   | 0.20    | 5.0              | 0.7    |
| 20/80                 | 6/24   | 4/16   | 0.25    | 4.0              | 0.6    |
| 20/63                 | 6/20   | 4/12.6 | 0.32    | 3.2              | 0.5    |
| 20/50                 | 6/15   | 4/10   | 0.40    | 2.5              | 0.4    |
| 20/40                 | 6/12   | 4/8    | 0.50    | 2.0              | 0.3    |
| 20/32                 | 6/10   | 4/6.4  | 0.63    | 1.6              | 0.2    |
| 20/25                 | 6/7.5  | 4/5    | 0.80    | 1.25             | 0.1    |
| 20/20                 | 6/6    | 4/4    | 1.0     | 1.0              | 0      |
| 20/16                 | 6/5    | 4/3.2  | 1.25    | 0.8              | - 0.1  |
| 20/12.5               | 6/3.75 | 4/2.5  | 1.60    | 0.63             | - 0.2  |
| 20/10                 | 6/3    | 4/2    | 2.0     | 0.5              | - 0.3  |

Snellen Visual Acuity in meters and feet, decimal notation, MAR, and logMAR.

ETDRS charts are based on linear LogMAR score.

a MAR, minimal angle of resolution (minute of arc).

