#### **2.2.2.2. Safety Endpoints**

- Adverse events, including monitoring of targeted events including, but not limited to:
  - Anticholinergic effects such as dry mouth, dry eyes and constipation.
  - CNS effects such as behavioral changes (eg, aggression), decreased cognitive function, headache, seizures, somnolence.

- Visual effects such as accommodation disorder, blurred vision, and amblyopia.
- Visual acuity and accommodation tests.
- Cognitive function by the Child Behavior Check List and Grooved Pegboard Test.
- Vital Signs, including heart rate in the context of age-appropriate norms.
- Urinary Tract Infection, as evidenced by urinalysis, urine microscopy, culture and sensitivity.
- Clinical Laboratory Evaluations in the context of age-appropriate norms, with particular reference to liver function tests and renal chemistry.
- Post-void residual volume (PVR) in subjects not performing CIC, or with >1 urinary tract infection (UTI) during the study.

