#### 4.1. Inclusion Criteria

Subject eligibility should be reviewed and documented by an appropriately qualified member of the investigator's study team before subjects are included in the study.

Subjects must meet all of the following inclusion criteria to be eligible for enrollment into the study:

1. Male or female subjects aged 6-17 years 11 months (age at time of first dose); that is subjects who have passed their sixth birthday but not reached their eighteenth birthday.
2. Subjects with stable neurological disease and clinically- or urodynamically-demonstrated NDO, confirmed urodynamically at Visit 2, by detrusor overactivity or decreased bladder compliance, with decreased maximum cystometric bladder capacity.

NOTE: Subjects with hypocontractile bladder, detrusor underactivity, or a 'flaccid' bladder should not be included.

3. Evidence of a personally signed and dated informed consent document indicating that the subject (or a legal representative) has been informed of all pertinent aspects of the study. In addition, an assent from the subject will be obtained when appropriate, and when the potential subject is capable of providing assent.
4. Female subjects who are of child-bearing potential (defined as  $\geq 9$  years old or have experienced menarche, whichever is earlier) must not be intending to become pregnant, currently pregnant, or lactating. The following conditions apply:
  - a. Subjects of childbearing potential must have a confirmed negative pregnancy test prior to randomization.
  - b. Subjects of child-bearing potential must agree to use effective contraception during the period of the trial and for at least 28 days after completion of treatment. Effective contraception includes abstinence.
  - c. Sexually active male subjects must agree to use effective contraception during the period of the trial and for at least 28 days after completion of treatment.

Further details of the definition of child-bearing potential and effective contraception may be found in Section 4.4.

5. Swallowing:
  - a. Subjects  $>25$  kg must already have the ability to swallow tablets whole, without chewing or crushing. The first dose of medication will be given in clinic under observation, and any subject not able to swallow tablets will be excluded from the study.

- b. Subjects  $\leq 25$  kg can either swallow the capsules whole or sprinkle on food.

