## **7.2. Safety Assessments**

### **7.2.1. Vital Signs**

Blood pressure, temperature and pulse rate should be measured at Visit 1, Visit 2, Visit 3, Visit 5 and Visit 7. This schedule of measurements should provide adequate indication of any clinically relevant changes. However, if vital signs show a clinically relevant change from baseline, then safety monitoring will occur at a minimum of monthly intervals, or more frequently as clinically appropriate, until the abnormality resolves. The measured results will be assessed in the context of age appropriate norms.

Temperature may be taken via oral, tympanic or axillary routes as per local accepted practice. Digital devices are permitted; however, mercury thermometers should not be used. The same method should be used for the subject throughout the study.

Blood pressure should be measured using a pediatric or appropriately sized sphygmomanometer in the sitting/resting position with the subject's arm supported at the level of the heart, and recorded to the nearest mmHg. The same arm (preferably the dominant arm) will be used throughout the study.

The same size blood pressure cuff, which has been properly sized and calibrated, will be used to measure blood pressure each time. The use of automated devices for measuring BP and pulse rate are acceptable, although, when done manually, pulse rate will be measured in the brachial/radial artery for at least 30 seconds.

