### **6.4. Covariates**

The baseline observation for the endpoint being analyzed will be used as a continuous covariate in any ANCOVA analyses.

Baseline weight will be used as a continuous endpoint in any ANCOVA analyses.

The following subgroups will be assessed for the primary endpoint:

Age: Ages  $\geq 6-9$ ,  $\geq 10-12$ ,  $\geq 13-17$

Weight: Cohort 1:  $\leq 50$  kg,  $>50$  kg, Cohort 2:  $\leq 20$  kg,  $>20$  kg

Gender: Male, Female

Region: Cohort 1: North America, Europe, Asia, Cohort 2: North America and Europe, Asia

Type of Underlying Disease: Congenital, Acquired, Unknown

Race: White, Asian, Black, Other (where Other includes: American Indian or Alaska Native, Native Hawaiian or other Pacific Islander)

Ethnicity: Hispanic/Latino, Not Hispanic/Latino

Underlying disease will be categorised as 'congenital' or 'acquired' and will be determined through manual review of medical history listings (by the clinician) for Cohort 1. If this is unable to be determined, this will be categorized as 'Unknown'. For Cohort 2 the answer to the question "Underlying Cause of Primary Diagnosis" on the Primary Diagnosis eCRF page will be utilized, for which the responses are 'Congenital' or 'Acquired'.

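### The three absolute vital-sign cut-offs in SAP 8.2.5 are the same at every age from 6 to 17, although protocol and SAP say vital signs are read against age-appropriate norms

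*SAP*

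**What the plan says.** Protocol 2.2.2.2 lists as a safety endpoint "Vital Signs, including heart rate in the context of age-appropriate norms", and SAP 6.2 repeats it. Protocol 7.2.1 adds "The measured results will be assessed in the context of age appropriate norms", which SAP 6.2.2 carries over.

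The planned analysis is in SAP 8.2.5 under Vital Sign Reporting. It consists of a summary of changes since baseline and a report of "the number of subjects whose blood pressure and heart rate fall outside specified ranges". The table beneath it gives these rows:

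- absolute values: SBP <90, DBP <50, pulse <40 or >120;
- changes from baseline: SBP up by 30 or more, SBP down by 30 or more, DBP up by 20 or more, DBP down by 20 or more.

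The counts of change are confined to blood pressure: "Furthermore, the number of subjects who decreases and increases in responses fall outside specified ranges will be summarized (for blood pressure only". One list serves Cohort 1 (>25 kg) and Cohort 2 (≤25 kg).

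**The concern.** A count of children outside a range is useful only if being outside means something. The documents say what it should mean here: a value that is unusual for the child's age. A limit that is constant from 6 to 17 years cannot carry that meaning at every age. The same pulse or systolic reading may sit differently against the norm for a 6-year-old and for a 17-year-old, but the table treats them alike.

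Heart rate is the one vital sign that the endpoint names. Both treatments in the trial are antimuscarinics, and safety is part of both primary objectives (protocol 2.1.1). A reader of the final tables could take the outlier counts to be the age-referenced assessment that the endpoint describes, when they are not.

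**Working it through.** No power, sample-size or error-rate figure is involved. The check sets the stated endpoint beside the planned tables.

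**1. What is promised.** Four places (protocol 2.2.2.2 and 7.2.1, SAP 6.2 and 6.2.2) tie vital signs to norms for age. None names a reference, percentile, z-score or limit.

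**2. The age range.** Protocol 4.1 admits children from the sixth birthday up to, but not including, the eighteenth. That is 17 − 6 + 1 = 12 single-year ages.

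**3. What the cut-off table contains.**

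- Rows in total: 7.
- Rows that vary with age, weight or cohort: 0.
- Absolute rows: 3 (SBP, DBP, pulse). Both blood-pressure rows are lower limits only.
- Change rows: 7 − 3 = 4, all for blood pressure and none for pulse.

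The promise of age norms bears on the 3 absolute rows. The 4 change rows compare each child with his or her own baseline, and nothing in the documents calls for age-specific limits there.

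**4. Whether another planned table supplies the age context.**

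- SAP 6.4 defines age groups, but introduces them with "The following subgroups will be assessed for the primary endpoint", which is an efficacy measure.
- SAP 8.2.5 lays out the other safety summaries by treatment sequence, with no age stratum.
- Protocol 9.3 says only that vital signs will be shown descriptively by treatment group.

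None of these applies an age norm to vital signs.

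**5. A secondary observation on what the counts pick up.** These two cases are illustrations, not predicted frequencies, and imply no clinical judgement.

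- Pulse rising from 70 to 115 is a change of 115 − 70 = +45. It enters no category, because 115 is not above 120 and there is no pulse-change row.
- SBP rising from 125 to 150 is a change of 150 − 125 = +25. It enters no category, because there is no upper limit and 25 is below 30.

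Both changes would still enter the continuous change-from-baseline summary. The descriptive statistics in SAP 8.1.1 include the minimum and maximum, so a +45 would appear as the maximum if it were the largest rise in its group.

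**The case against.** The strongest reply is that the outlier table need not be where age norms are applied. The sentence in protocol 7.2.1 stands next to a rule for closer monitoring after a clinically relevant change, so it can be read as case-level assessment by the investigator. Abnormal findings that meet the criteria in protocol 8.4 reach the adverse-event tables. The EDMC reviews vital signs (protocol 9.5). Safety tables follow sponsor standards that are not in the documents and might add age-based displays. All of this stands as possibility. None of it is written down as the place where age norms enter the analysis. In the EDMC text the age-norm phrase is attached to the laboratory evaluations, and for vital signs the SAP sets out its own fixed list.

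A reader might also infer more than the documents support:

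- **That every outlier count is affected.** The four change rows are within-subject and need no age norm.
- **That the endpoint requires a category for heart-rate change.** The wording asks for age context, which a change category would not supply. Pulse change is also already summarised as a continuous variable.
- **That the endpoint requires an upper blood-pressure limit.** No passage says so, and the rows for increases capture some rises.
- **That the endpoint cannot be assessed at all.** Review against norms by investigators or the EDMC is not excluded.

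**Conclusion.** The point holds in a narrow form. The three absolute limits for SBP, DBP and pulse do not vary by age, so these counts, as specified, do not classify values against age norms as the endpoint wording says. The gap is 3 of 7 rows, in both cohorts. It cannot be sized further: that would need the paediatric norms and the observed values, and the documents give neither.

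The missing pulse-change and high-blood-pressure counts are a separate and weaker matter. They limit what the tables pick up, but they do not contradict the endpoint.

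The conclusion assumes that the unseen sponsor standards do not already add an age-based display. If they do, a sentence in the SAP pointing to it would settle the matter. The effect is confined to descriptive safety tables.

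**What to change.** Before database release:

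1. Name a paediatric reference in SAP 8.2.5 and tabulate the absolute SBP, DBP and pulse counts against its age-specific limits. The fixed cut-offs can stay as a supplementary display. State whether age at first dose or age at each visit is used.
2. If no reference is adopted, reword the endpoint to match the tables, or state who applies the norms, with which reference, and where the result is reported.
3. Optionally, add a categorical table of pulse change from baseline and a count of high absolute blood pressure, with limits chosen and justified by the sponsor.

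The age bands in SAP 6.4 should not be borrowed without thought, because they were set for subgroups of the primary endpoint. The bands should follow the chosen reference. The Schedule of Activities includes weight but no height measurement, so a reference that needs height may not be usable.

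The cost is the choice of a reference and a little table programming. Vital signs are already recorded at five visits (protocol 7.2.1), and date of birth is collected. No new data, visits or change to the primary analysis are needed.

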### **7.2.4. Visual Acuity and Accommodation**

Visual acuity will be assessed for each eye using the Snellen method, using an optotype that is appropriate to the child's intellectual development at Visit 2, Visit 5, and Visit 7.

Amplitude of accommodation will be assessed by the push up test to assess minimum focusing distance at Visit 2, Visit 5, and Visit 7. The subject will focus on a single letter of the 20/40 line of an eye chart (appropriate optotype) and this will be moved slowly toward the subject until it blurs. At this point the distance from eye to letter will be measured. An attempt will be made to record 3 measurements and entered in the eCRF.

For both visual acuity and accommodation assessments the same optotype will be used for a specific subject throughout the study to ensure standardization and validity.

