### **7.2.9. Grooved Pegboard Test (GPT)**

The Grooved Pegboard Test is a manipulative dexterity test that assesses psychomotor speed, fine motor control, and rapid-visual motor coordination. It consists of a small board of 25 holes with randomly positioned slots. Pegs with a key along one side must be rotated to match the hole before they can be inserted. Time to completion, number of pegs dropped, and number of pegs placed correctly are scored.

The GPT will be assessed at Visit 2, Visit 5 and Visit 7.

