### **8.1.1. Analysis of Continuous Data**

Where data is to be summarized using descriptive statistics the following will be presented: n, mean, standard deviation, median, minimum, and maximum.

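### Accommodation is summarised only as raw blur distance, so the same optical loss can give very different changes in cm; add a summary in dioptres beside it

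*SAP*

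**What the plan says.** Protocol 7.2.4 states: "Amplitude of accommodation will be assessed by the push up test to assess minimum focusing distance". A letter is moved towards the child until it blurs, and then "At this point the distance from eye to letter will be measured". Sites are to attempt three readings. The SAP's own description of the test, in section 6.2, agrees and specifies each eye.

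For the analysis, SAP 8.2.5 (Vital Sign Reporting) defines the variable as "Accommodation (the distance for each eye at which vision becomes blurred", taken as the mean of three readings. With the other vision and function measures, it "will be summarized by visit and changes from baseline at each visit using descriptive statistics". SAP 8.1.1 lists these statistics as "n, mean, standard deviation, median, minimum, and maximum". No test is planned.

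Visual acuity is treated differently in the same section: "For Visual Acuity, LogMAR units will be derived from the Snellen ratios recorded on the CRF", with a conversion table. Neither document gives a conversion for accommodation, a baseline near point or an expected change.

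**The concern.** The construct that the protocol names and the variable that the SAP averages are reciprocals of each other. A drug that removes the same amount of focusing power from every child would move the blur point by a millimetre or two in some and by many centimetres in others. A mean and SD of change in cm then reflect which children are in the group as well as what the drug did.

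This has some practical weight. Protocol 2.2.2.2 names accommodation disorder among the targeted visual effects, and Protocol 9.5 lists vision testing among the data that the monitoring committee sees. With no test planned, the table is the evidence, and its scale decides how a loss appears. The SAP already rescales acuity before averaging it, so the step would not be foreign to this section.

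**Working it through.** **Inputs.** The documents contain no figure for accommodation, so there is nothing of the plan's own to reproduce. The only outside element is the optical definition, dioptres (D) = 100/distance in cm. All baselines and losses below are assumptions. The group size of 33 is the evaluable number per Cohort 1 arm in Protocol 9.1, used for scale only.

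**1. Change in cm for an equal loss.** A child with baseline amplitude A who loses L dioptres moves from 100/A to 100/(A − L) cm. With L = 2 D:

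| Baseline (D) | Before (cm) | After (cm) | Change (cm) |
|---|---|---|---|
| 20 | 5.00 | 5.56 | +0.56 |
| 16 | 6.25 | 7.14 | +0.89 |
| 12 | 8.33 | 10.00 | +1.67 |
| 10 | 10.00 | 12.50 | +2.50 |
| 6 | 16.67 | 25.00 | +8.33 |
| 5 | 20.00 | 33.33 | +13.33 |
| 4 | 25.00 | 50.00 | +25.00 |

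Ratios from unrounded values:
- 12 against 10 D: 1.5
- 12 against 6 D: 5.0
- 12 against 5 D: 8.0
- 12 against 4 D: 15.0
- 16 against 4 D: 28.0
- 20 against 4 D: 45.0

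Other losses give a similar picture. At 1 D, 12 against 5 D gives 6.6 and 16 against 4 D gives 20.0. At 3 D, 12 against 6 D gives 6.0 and 16 against 5 D gives 20.8. In dioptres the ratio is 1.0 by construction.

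**2. Effect on a group summary.** Suppose 30 children start at 7 cm, 3 start at 20 cm, and all lose 3 D.
- From 7 cm: 100/7 = 14.29 D; 14.29 − 3 = 11.29 D; 100/11.29 = 8.86 cm; change +1.86 cm.
- From 20 cm: 5 D − 3 D = 2 D; 100/2 = 50 cm; change +30 cm.
- Mean: (30 × 1.86 + 3 × 30)/33 = 145.8/33 = 4.4 cm.
- Share from the 3 children: 90/145.8 = 62%.
- SD: √[(30 × 3/33) × (30 − 1.86)² / 32] = 8.2 cm.
- Median: +1.86 cm.

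In dioptres every child changes by −3, so the mean is −3 and the SD is 0.

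A milder mix has 32 children at 12 D and one at 4 D, all losing 2 D. The mean is (32 × 1.67 + 25)/33 = 2.37 cm, against 1.67 cm without that child's influence. The median stays at 1.67 cm.

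**3. What the median leaves.** In the first mix the median is not distorted by the three outlying children. It shows +1.86 cm for children who lost 3/14.29 = 21% of their amplitude, while the same loss is +30 cm for a child who started at 20 cm.

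**4. Reading error on the reciprocal scale.** A 1 cm error at 6 cm is 100/6 − 100/7 = 2.4 D. At 20 cm it is 100/20 − 100/21 = 0.24 D.

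**5. Order of averaging.** Readings of 6, 8 and 10 cm give 100/8 = 12.5 D if averaged first. Converted first, they give (16.67 + 12.5 + 10)/3 = 13.06 D. The SAP should therefore state the order.

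**The case against.** The best defence is that the SAP summarises what the protocol measures: the test is there to find a minimum focusing distance, and a distance is what is recorded. That stands. The distance table is legitimate and should stay.

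The next point is that the median, minimum and maximum are already planned. This stands in part. The median resists a few long near points and the maximum shows them, but neither puts children with different baselines on a common scale.

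Thirdly, dioptres have the mirror-image weakness. By step 4, the same reading error is about ten times larger at 6 cm than at 20 cm, and it falls on the short-near-point children whose losses the conversion is meant to reveal. This stands in full and is why dioptres should not replace distance.

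Fourthly, little depends on this table. Accommodation disorder and blurred vision are also captured as adverse events, Protocol 7.2.2 has clinically significant worsening on examination recorded as an adverse event, and the SAP calls its safety analysis exploratory. That stands and limits the severity.

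A reader might infer three stronger things that the documents do not support.
- **That equal losses will look more than 20-fold different.** No near points are given. Ratios that large need widely spaced baselines, such as 16 against 4 D, and nearer baselines give far less.
- **That a uniform loss would be invisible.** In the mix in step 2 the planned median still shows +1.86 cm on a 7 cm baseline, or 27%. Compressed is the accurate word.
- **That the Grooved Pegboard summary has a comparable scale fault.** Protocol 7.2.9 says "Time to completion, number of pegs dropped, and number of pegs placed correctly are scored", and SAP 8.2.5 tabulates all three, by hand and by "whether the 10-peg or 25-peg test was used, separately". Neither document describes a time limit, abandoned tests or children changing version, so a loss of slow performers from the time summary is inference, and a shortfall would appear in the peg count. The lack of a rule for an unfinished test is missing detail in an untested descriptive table. Pegs per minute would not repair it, since it cannot be calculated when the time is missing.

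**Conclusion.** The point holds in a limited form. Averaging raw distance without also reporting amplitude leaves a summary whose mean and SD can be driven by a few children with long near points, and in which losses among children with short near points look small. For an assumed 2 D loss the disparity between two children is about 1.5-fold to 45-fold, and where the trial would fall in that range depends on baselines that the documents do not give. The direction follows from the reciprocal relation; the size is an assumption. The primary endpoint and all hypothesis tests are unaffected. This is an optional improvement to a descriptive safety table.

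**What to change.** In SAP 8.2.5, add a derivation: convert each recorded blur distance to dioptres (100/cm), average the available readings for each eye, and summarise amplitude and its change from baseline by visit with mean, SD, median, minimum and maximum. Present this beside the planned distance summary, with a note that dioptres are more sensitive to reading error at short distances, so the median should be read with the mean. Referring to available readings also covers a child with fewer than three, since the protocol asks only for an attempt at three.

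If the section is being edited anyway, it could say that pegboard change is calculated only between tests of the same version. That merely clarifies the existing split.

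The cost is one derived variable from data already collected, extra table rows and a short SAP wording change, best made before database release. No assessment, visit or sample size changes.
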